# Figure 4. Example index tofacitinib dispensing and patient-specific study period against the VTE Reporting Periods

The 12-month **baseline period** will immediately precede the patient's index date and will be used to ascertain indication (including off-label indications), comorbidities, prior and current medications, potential contraindicated use of tofacitinib, VTE risk factors, use in patients aged 65 years and older, CV risk factors, malignancy risk factors, and whether there is evidence that prescribers are following the recommended screenings in the aRMM materials that should occur *prior to* initiation of tofacitinib.

The 12-month **follow-up period** will begin on the patient's index date and will be used to ascertain comorbidities, comedications, compliance to the recommended posology per indication (ADD) and duration of tofacitinib treatment, potential contraindicated use of tofacitinib, VTE risk factors, CV risk factors, malignancy risk factors, use with concomitant medications not compatible with tofacitinib, and whether there is evidence that prescribers are following the recommended monitoring in the aRMM materials that should occur *after* initiation of tofacitinib.

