- Compliance to patient screening and laboratory monitoring prior to and during tofacitinib treatment, as measured by:h
  - The proportion of patients with evidence of having received the following recommended screenings *prior to* initiation of tofacitinib:
    - Creatinine (serum or urine) laboratory testing;
    - TB screening;
    - Viral hepatitis B and C screening;
    - ALC laboratory testing;
    - ANC laboratory testing;
    - Haemoglobin laboratory testing; and

<sup>g Hungary will not have a VTE Reporting Period 1. Hungary will also not have a VTE Reporting Period 2 for PsA and UC.

<sup>h This outcome (and all sub-outcomes) will *not* be assessed in Sweden because the Swedish national health registers do not capture the laboratory tests of interest. In GKV claims, it may not be possible to differentiate an ALC laboratory test from an ANC laboratory test, or an ALT laboratory test from an AST laboratory test. In the PHARMO Database Network, TB screening and viral hepatitis B and C testing are not captured.

- ALT and/or AST laboratory testing (i.e., liver function testing);
- For patients with 6 and 12 months of tofacitinib therapy, the proportion of patients with evidence of having received the following recommended monitoring *after* initiation of tofacitinib in the respective periods:
  - TB screening;
  - Viral hepatitis B and C screening;
  - ALC laboratory testing;
  - ANC laboratory testing;
  - Haemoglobin laboratory testing;
  - ALT and/or AST laboratory testing; and
  - Lipid panel (i.e., total cholesterol, high-density lipoprotein [HDL], lowdensity lipoprotein [LDL], and triglycerides [TG]) laboratory testing;
- Compliance to recommendations to limitations for use, including
  - Use in patients with VTE risk factors, as measured by:e
    - The proportion of patients with evidence of  $\geq 1$  VTE risk factors *prior to* initiation of tofacitinib, reported overall and by approved indication;
    - The number of VTE risk factors identified *prior to* initiation of tofacitinib, reported overall and by approved indication;
    - The proportion of patients with UC who have: ≥1 VTE risk factor identified *prior to* tofacitinib initiation; no use of an alternative therapy (i.e., biologic) *prior to* tofacitinib initiation; and an ADD >10 mg in Weeks 16-23, Weeks 24-31, Weeks 32-39; and Weeks 40-47 of follow-up;f

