- In the 30 days prior to and including the day of tofacitinib initiation;
- In the 31 to 60 days prior to tofacitinib initiation;
- In the 61 to 90 days prior to tofacitinib initiation;
- In the 91 to 180 days prior to tofacitinib initiation;

For patients with 6 months of tofacitinib therapy (duration of tofacitinib therapy defined in Section 9.3.3):

- In the 60 days after and including the day of tofacitinib initiation;
- In the 61 to 120 days after tofacitinib initiation; and
- In the 121 to 180 days after tofacitinib initiation.

For patients with 12 months of tofacitinib therapy (duration of tofacitinib therapy defined in Section 9.3.3):

- In the 181 to 240 days after tofacitinib initiation;
- In the 241 to 300 days after tofacitinib initiation; and
- In the 301 to 360 days after tofacitinib initiation.

For analyses, 1 month will be defined as 30 days and 1 year will be defined as 360 days.

Timeframes for the baseline period are mutually exclusive. For patients with multiple procedure and/or diagnosis codes during the baseline period, the procedure or diagnosis code occurring closest to the index tofacitinib prescription dispensing will be selected.

<sup>u This outcome (and all sub-outcomes) will *not* be assessed in Sweden because the Swedish national health registers do not capture the laboratory tests of interest. In GKV claims, it may not be possible to differentiate an ALC laboratory test from an ANC laboratory test, or an ALT laboratory test from an AST laboratory test. In the PHARMO Database Network, TB screening and viral hepatitis B and C testing are not captured.

Variable	Role	Operational definition		
Creatinine (serum or urine) laboratory testing	Outcome: Screening	Defined as $\geq 1$ procedure code or $\geq 1$ ICD- 10 diagnosis code for a creatinine (serum or urine) laboratory test.		
TB screening	Outcome: Screening	Defined as $\geq 1$ procedure code or $\geq 1$ ICD-		
	Outcome: Monitoring	10 diagnosis code for TB (active and latent) screening.		
Viral hepatitis B and C	Outcome: Screening	Defined as $\geq 1$ procedure code or $\geq 1$ ICD-		
screening	Outcome: Monitoring	and C screening.		
Absolute lymphocyte	Outcome: Screening	Defined as $\geq 1$ procedure code or $\geq 1$ ICD-		
count (ALC) laboratory testing	Outcome: Monitoring	10 diagnosis code for ALC laboratory testing.		
Absolute neutrophil count	Outcome: Screening	Defined as $\geq 1$ procedure code or $\geq 1$ ICD-		

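### The index day sits in both the nearest screening window and the first monitoring window, so one test dated that day counts as both and early monitoring can only be overstated

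*Protocol*

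**What the plan says.** Table 3 in Section 9.3.2 lists four screening windows and six monitoring windows. The screening window nearest to treatment is "In the 30 days prior to and including the day of tofacitinib initiation". The first monitoring window is "In the 60 days after and including the day of tofacitinib initiation", and it applies under the heading "For patients with 6 months of tofacitinib therapy (duration of tofacitinib therapy defined in Section 9.3.3").

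Two rules follow. The first is "Timeframes for the baseline period are mutually exclusive". The second, which picks the code nearest the index dispensing, begins "For patients with multiple procedure and/or diagnosis codes during the baseline period". Neither addresses a screening window against a monitoring window.

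Section 9.3.1 separates the two outcomes by time: screening is received before initiation, and the monitoring outcome, "the proportion of patients with evidence of having received the following recommended monitoring", concerns tests after it. Section 9.2.3 makes the same split. It also says that the baseline period "will immediately precede the patient's index date" and that the follow-up period "will begin on the patient's index date and will be used to ascertain comorbidities", among other things.

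**The concern.** The day of initiation belongs to two windows that feed two different outcomes, and nothing in the protocol stops the same code from being used for both. For six test rows in Table 3 (TB, hepatitis B and C, ALC, ANC, haemoglobin, ALT and/or AST), one code is enough and the row carries both the screening and the monitoring role. The closest-code rule makes an index-day code the chosen screening test, and the same code then satisfies the first monitoring window.

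The lipid panel is a monitoring outcome only, so it is not counted twice. A panel dated on the index day is still credited as monitoring after initiation.

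Compliance with laboratory monitoring is part of Primary Objective 2. The error runs one way: a patient with an index-day test and no later test in the window is reported as monitored. A larger sample does not reduce it.

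**Working it through.** **Window check.** Number the days relative to initiation, with the index date as day 0, and write each Table 3 timeframe as a set of days.

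| Window | Days | Length |
|---|---|---|
| Screening, nearest | -30 to 0 | 31 |
| Screening, next three | -60 to -31; -90 to -61; -180 to -91 | 30; 30; 90 |
| Monitoring, first | 0 to 60 | 61 |
| Monitoring, next five | 61-120; 121-180; 181-240; 241-300; 301-360 | 60 each |

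The first monitoring window is taken to run through day 60 because the next one starts at day 61. Intersecting all pairs of the ten windows gives exactly one overlap: the nearest screening window and the first monitoring window share day 0. If monitoring starts on the day after the index date, that intersection is empty and the first monitoring window has 60 days, like the other five.

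**Against the protocol's own definitions.** Section 9.2.3 assigns the index date to one period only, since baseline precedes it and follow-up begins on it. Table 3 assigns it to both sides. Sections 9.2.3 and 9.3.1 describe monitoring as occurring after initiation, which an index-day code does not satisfy in the ordinary sense.

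**Size.** The protocol states no figure to reproduce. Let m be the share truly tested on days 1 to 60 and q the share with a test dated on day 0. Both are assumptions.

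- In general, reported proportion = m + P(tested on day 0 and not on days 1 to 60).
- If the two are independent, this is m + (1 - m)q.

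| m | q = 10% | q = 20% | q = 30% |
|---|---|---|---|
| 60% | 0.60 + 0.40 × 0.10 = 64% | 0.60 + 0.40 × 0.20 = 68% | 0.60 + 0.40 × 0.30 = 72% |
| 40% | 0.40 + 0.60 × 0.10 = 46% | 0.40 + 0.60 × 0.20 = 52% | 0.40 + 0.60 × 0.30 = 58% |

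Without independence, the added share lies between max(0, q - m) and min(q, 1 - m). For m = 40% and q = 30%, that is 0 to 30 points. It is zero if everyone tested on day 0 is also tested on days 1 to 60.

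**The case against.** The strongest reply is that the monitoring window is not the part that departs from the general definitions. Section 9.2.3 starts follow-up on the index date, so including that day in monitoring is consistent with it; the screening window is the one that reaches across. This stands as a point about where the inconsistency arises. It does not remove the overlap, and Sections 9.2.3 and 9.3.1 still describe monitoring as occurring after initiation. It does mean that giving the day to screening needs to be stated as a deliberate exception.

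The reach of the problem is also limited, and these limits stand:

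- It touches one of six monitoring windows; screening proportions are not inflated.
- It applies only to patients with 6 months of therapy.
- Sweden is not assessed for this outcome, and PHARMO captures no TB or hepatitis testing. Only 40% of PHARMO's tofacitinib patients are also in its laboratory database (Table 9, note a).
- In the German claims, outpatient diagnoses carry only a quarter, so a one-day boundary cannot be resolved for tests identified by an outpatient diagnosis code.

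A reader might infer that prescribers are credited for any test at the visit where treatment was decided. The documents do not support that: the index date is the first dispensing (Section 9.2.3), and a test at an earlier prescribing visit falls in screening alone. A reader might also infer that Hungary is worst affected because tofacitinib goes through the hospital channel there. Section 9.9 mentions that channel to explain the missing milligram information and says nothing about testing and dispensing on the same day.

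Finally, it could be said that the statistical analysis plan will settle this. Section 9.3.2 leaves final algorithms and code lists to that plan, but the day boundaries are already stated in the protocol, and following them as written carries the overlap forward.

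**Conclusion.** The point holds as a one-day overlap with a one-directional effect. As written, an index-day code for any of the six dual-role tests counts as screening and as monitoring, and an index-day lipid panel counts as monitoring. The first-window monitoring proportion can only be raised, among patients with 6 months of therapy, in Hungary, Germany and, for the tests that PHARMO captures, the Netherlands.

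The size is not known. It would be tempting to read the illustrative figures as an overstatement of 4 to 18 points in this study; they are not an estimate of it. They rest on assumed values of m and q and on independence, and no document gives the frequency of testing on the dispensing day. If few patients are tested that day, or if those who are get retested within 60 days, the bias is close to zero. The case for correction is that the rule conflicts with the protocol's description of monitoring and is simple to repair.

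**What to change.** In Table 3, keep the index date in the nearest screening window only. Start the first monitoring window on the day after the index date and run it through 60 days after the index date, for every test including the lipid panel. Add that a test counted as screening cannot also count as monitoring.

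Use the words *day after the index date* rather than *day 1*: Section 9.3.4 counts from the index date and labels its first interval from Day 1, so *day 1* could be read as the very day to be excluded. Note that this is a deliberate exception to Section 9.2.3, where follow-up begins on the index date, and carry the same wording into the statistical analysis plan.

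The cost is a small wording change with no new data. The reported early monitoring proportion will be slightly lower.

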History of malignancy (non-metastatic and metastatic; excluding non- melanoma skin cancer)	Outcome: VTE risk factor	Defined as ≥1 ICD-10 diagnosis code for malignancy (excluding non-melanoma skin cancer) in the 12 months prior to or on the day of the index tofacitinib dispensing.
Age >50 years at tofacitinib initiation	Outcome: VTE risk factor	Defined as age at tofacitinib initiation >50 years.
History of diabetes	Outcome: VTE risk factor	Defined as $\geq 1$ ICD-10 diagnosis code for diabetes in the 12 months prior to or on the day of the index tofacitinib dispensing.
History of hypertension	Outcome: VTE risk factor	Defined as ≥1 ICD-10 diagnosis code for hypertension in the 12 months prior to or on the day of the index tofacitinib dispensing.
Initiating tofacitinib with ≥1 VTE risk factor	Outcome: VTE risk factor	Defined as ≥1 VTE risk factor (as listed and defined above) identified in the 12 months prior to or on the day of the index tofacitinib dispensing (unless otherwise specified).
Number of VTE risk factors identified prior to tofacitinib initiation	Outcome: VTE risk factor	Calculated as the sum of the number of VTE risk factors (as listed and defined above) identified in the 12 months prior to or on the day of the index tofacitinib dispensing (unless otherwise specified).

Table 3.	Operational	definitions of	f study	variables in	the selected	databases
----------	-------------	----------------	---------	--------------	--------------	-----------

Variable	Role	Operational definition
Number of UC patients with: ≥1 VTE risk factor; no prior alternative therapy (i.e., biologic); and an ADD >10 mg in Weeks 16-23, Weeks 24- 31, Weeks 32-39, and Weeks 40-47 of follow-up t	Outcome: VTE risk factor	Defined as a patient meeting all of the following criteria: ≥1 ICD-10 diagnosis code for UC; ≥1 VTE risk factor (as listed and defined above); 0 prescription medication dispensings for a biologic (as identified by ATC codes) in the 12 months prior to and including the date of the index tofacitinib prescription dispensing; and an ADD of >10 mg in Weeks 16-23, Weeks 24-31, Weeks 32- 39, and Weeks 40-47 of follow-up, respectively (ADD defined in Section 9.3.4). Complete list of biologics in ANNEX 6. LIST OF ATC CODES FOR MEDICATIONS OF INTEREST TO AVOID WHILE TAKING TOFACITINIB.

 Table 3.
 Operational definitions of study variables in the selected databases

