### 9.7.1.2.2.1. Compliance to recommendations for limitations of use

### 9.7.1.2.2.1.1. Patients with VTE risk factors

The proportion of patients with one or more risk factors for VTE, identified prior to tofacitinib initiation, will be described and tabulated overall and by individual VTE risk factor (e.g., prior VTE, recent MI). Proportions will be stratified by "RA or PsA" and "UC."

The total number of VTE risk factors identified prior to tofacitinib initiation will also be described continuously and stratified by "RA or PsA" and "UC."

The proportion of patients diagnosed with UC, one or more VTE risk factors identified prior to tofacitinib initiation, and no use of an alternative therapy (i.e., biologic) prior to tofacitinib

<sup>oo The study outcomes that contain an ADD component will *not* be assessed in Hungary or the Netherlands. The Hungarian administrative claims database is unable to estimate ADD, either directly or by proxy, due to how tofacitinib is captured in the database. In the high-budget impact medication dataset of the PHARMO Database Network (Netherlands), neither ADD nor the number of pills per prescription is captured.

<sup>pp In GKV claims, outpatient diagnoses are reported quarterly.

<sup>qq Hungary will not have a VTE Reporting Period 1. Hungary will also not have a VTE Reporting Period 2 for PsA and UC.

<sup>IT This outcome (and all sub-outcomes) will not be assessed in Sweden because the Swedish national health registers do not capture the laboratory tests of interest. In GKV claims, it may not be possible to differentiate an ALC laboratory test from an ANC laboratory test, or an ALT laboratory test from an AST laboratory test. In the PHARMO Database Network, TB screening and viral hepatitis B and C testing are not captured.

initiation whose ADD in Week 16 through Week 23, Week 24 through Week 31, Week 32 through Week 39, and Week 40 through Week 47 was >10 mg will be described and tabulated.

The proportion of patients who discontinue tofacitinib after developing one or more VTE risk factors while taking tofacitinib will be described and tabulated overall and by individual VTE risk factor (e.g., VTE, MI). Proportions will be stratified by "RA or PsA" and "UC."

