#### 9.7.1.3.1. Use in patients with VTE risk factors

The proportion of patients with one or more risk factors for VTE, identified prior to tofacitinib initiation, will be described and tabulated overall and for each individual VTE risk factor (e.g., prior VTE, recent MI) for VTE Reporting Period 1, VTE Reporting Period 2, and VTE Reporting Period 3.vv Proportions will be stratified by "RA or PsA" and "UC."

The total number of VTE risk factors identified prior to tofacitinib initiation will also be described continuously for VTE Reporting Period 1, VTE Reporting Period 2, and VTE Reporting Period 3vv and stratified by "RA or PsA" and "UC."

The proportion of patients diagnosed with UC, one or more VTE risk factors identified prior to tofacitinib initiation, and no use of an alternative therapy (i.e., biologic) prior to tofacitinib initiation whose ADD in Week 16 through Week 23, Week 24 through Week 31, Week 32 through Week 39, and Week 40 through Week 47 was >10 mg will be described and tabulated for VTE Reporting Period 1, VTE Reporting Period 2, and VTE Reporting Period 3.vv

The proportion of patients who discontinue tofacitinib after developing one or more VTE risk factors while taking tofacitinib will be described and tabulated overall and for each individual VTE risk factor (e.g., VTE, MI) for VTE Reporting Period 1, VTE Reporting

ss Patients with  $\geq 2$  dispensings of tofacitinib are more likely to have taken tofacitinib for the full days' supply of the prescription as opposed to patients with only 1 dispensing of tofacitinib.

<sup>tt The study outcomes that contain an ADD component will *not* be assessed in Hungary or the Netherlands. The Hungarian administrative claims database is unable to estimate ADD, either directly or by proxy, due to how tofacitinib is captured in the database. In the high-budget impact medication dataset of the PHARMO Database Network (Netherlands), neither ADD nor the number of pills per prescription is captured.

<sup>uu In GKV claims, outpatient diagnoses are reported quarterly.

<sup>vv Hungary will not have a VTE Reporting Period 1. Hungary will also not have a VTE Reporting Period 2 for PsA and UC.

<sup>ww Hungary will not have a CV and Malignancy Reporting Period 1 or a CV and Malignancy Reporting Period 2 for PsA and UC.

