discretion of the healthcare provider will be limited. For example, assessment of whether tofacitinib is being "used with caution in patients with known risk factors for VTE, regardless of indication and dosage" cannot be done directly in this study. This assessment will be approximated using the number and proportion of patients who had VTE risk factors ( $\geq 1$  and  $\geq 2$ ) and were prescribed tofacitinib before and after the 2019 Article 20 referral aRMM materials were implemented. However, this assessment is limited in the sense that if the proportion of patients with VTE risk factors prescribed tofacitinib does not decline over time, it does not necessarily mean that prescribers were not prescribing tofacitinib with caution among patients with VTE risk factors.

The results from this study may not be generalizable to other member states of the EU (e.g., prescribing patterns and implementation of the recommended screenings and monitorings may vary by country). Finally, only the RA indication has received full reimbursement in Hungary (in May 2019), with the PsA and UC indications available only via the Named Patient Program. Thus, Hungary will not have a VTE Reporting Period 1 for any indication and also will not have a VTE Reporting Period 2 for the PsA and UC indications, nor will Hungary have a CV and Malignancy Reporting Period 1 or a CV and Malignancy Reporting Period 2 for the PsA and UC indications, which limits the MAH's ability to examine changes in the utilisation of tofacitinib among patients with VTE risk factors, among elderly patients, and among patients with CV or malignancy risk factors in Hungary following the updated recommendations and limitations for use. Additionally, there may be smaller patient numbers for these two indications relative to the RA indication in Hungary. However, there will be more comprehensive data across indications from Sweden. In the Netherlands, the PHARMO Database Network requires linkage between different data sources. As the same patients may not be captured by all databases and the initial number of tofacitinib patients is not high, patient counts may be affected by linkage.

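### Age over 50 alone meets the composite of at least one VTE risk factor, so the composite confounds age mix with prescribing to patients who have other VTE risk factors, and no age-free version is planned

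*Protocol*

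**What the plan says.** Table 3 (Section 9.3.2) lists ten VTE risk factors before initiation. Nine are diagnoses, procedures or medicines. The tenth is age: "Defined as age at tofacitinib initiation >50 years". The composite needs any one of them: "Defined as ≥1 VTE risk factor (as listed and defined above) identified in the 12 months prior to or on the day of the index" dispensing.

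The composite is used in four places:

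- **Primary objective 2** (Sections 9.3.1 and 9.7.1.2.2.1.1): the proportion of initiators meeting it.
- **Secondary objective 2** (Section 9.7.1.3.1): "The proportion of patients with one or more risk factors for VTE, identified prior to tofacitinib initiation", which "will be described and tabulated overall and for each individual VTE risk factor (e.g., prior VTE, recent MI) for VTE Reporting Period 1" and likewise for Periods 2 and 3. The same section adds a count: "The total number of VTE risk factors identified prior to tofacitinib initiation will also be described continuously for VTE Reporting Period 1" and the later periods.
- **The UC dose outcome** (Table 3, Sections 9.7.1.2.2.1.1 and 9.7.1.3.1): UC patients with "one or more VTE risk factors identified prior to tofacitinib initiation, and no use of an alternative therapy" and an ADD above 10 mg in the later 8-week intervals.
- **ADD strata** (Sections 9.3.4 and 9.7.1.2.1): presence or absence of the composite.

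Section 9.9 explains how cautious use will be judged: "This assessment will be approximated using the number and proportion of patients who had VTE risk factors", at one or more and at two or more factors, before and after the 2019 materials. It warns that if the proportion does not decline, "it does not necessarily mean that prescribers were not prescribing tofacitinib with caution among patients with VTE risk factors". It does not mention that age alone meets the composite.

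**The concern.** The composite is meant to show whether prescribers became more careful with patients who have VTE risk factors. Every initiator over 50 meets it, whether or not any other factor is present. Two difficulties follow.

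First, reduced prescribing to patients with a non-age factor is diluted. A patient over 50 without such a factor stays in the numerator throughout.

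Second, a fall need not concern VTE. Section 7 says that the SmPC revision approved in January 2020 carried both the VTE warnings and the restriction at 65 years and older. The 2021 procedure again restricted use in older patients, inside VTE Reporting Period 3 (October 2020 to December 2023). Everyone covered by those age restrictions is over 50. Prescribers who followed only the age restrictions would lower the VTE composite, although use at 65 and older already has its own outcomes by period.

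**Working it through.** **The plan's own figure.** Section 9.5: n = 0.50 × 0.50 × 1.96² / 0.10² = 96.04, so 97, rounded up to 100. It reproduces. It sets precision for a proportion of 50% and does not depend on what the composite contains.

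**Inputs.** The protocol gives no age mix and no risk-factor prevalence, so all of these are assumed:

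- a = share of initiators over 50: 30%, 60% or 80%.
- y = share with a non-age factor at 50 or under: 15% (range 10% to 25%).
- o = share with a non-age factor over 50: 45% (range 30% to 55%).
- Scenario: half of the initiations in patients with a non-age factor no longer occur; all others are unchanged.

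**Formulas.** Composite as written: C = a + (1−a)y, which can never be below a. At least one non-age factor: N = (1−a)y + a·o. After the change the cohort shrinks to T = 1 − N/2. Then C becomes 1 − (1−a)(1−y)/T and N becomes (N/2)/T.

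**Worked case, a = 60%.** C = 0.60 + 0.40 × 0.15 = 0.660. N = 0.06 + 0.27 = 0.330. T = 1 − 0.165 = 0.835. C after = 1 − 0.34/0.835 = 0.593. N after = 0.165/0.835 = 0.198.

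| Share over 50 | Composite as written | Fall (points) | Non-age composite | Fall (points) | Change removed by the age item |
|---|---|---|---|---|---|
| 30% | 40.5% to 32.4% | 8.1 | 24.0% to 13.6% | 10.4 | 22% |
| 60% | 66.0% to 59.3% | 6.7 | 33.0% to 19.8% | 13.2 | 49% |
| 80% | 83.0% to 78.9% | 4.1 | 39.0% to 24.2% | 14.8 | 72% |

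**Why the last column behaves this way.** The fall in C is (1−a)(1−y)(1/T − 1), and the fall in N is (1−N)(1/T − 1). The fraction removed is therefore a(1−o) / [(1−a)(1−y) + a(1−o)], the share of patients without a non-age factor who are over 50: 0.165/0.760, 0.330/0.670 and 0.440/0.610. It does not depend on the halving, only on age mix and prevalence. Taking y/o as 10%/30% and 25%/55%, it runs from 20% to 25%, 47% to 54% and 71% to 76% for the three age mixes. Falls across these scenarios run from 2.7 to 10.8 points for the composite and 7.3 to 16.5 points for the non-age version.

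**Age mix alone.** With y and o fixed, each one-point drop in the share over 50 lowers C by 1 − y = 0.85 point and N by o − y = 0.30 point. The non-age version is less exposed to age mix, but not immune.

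**Against the protocol's precision.** At n = 100, the 95% half-width 1.96 × √[C(1−C)/100] is 9.6, 9.3 and 7.4 points at the three starting values of C. The composite's falls (8.1, 6.7, 4.1) lie inside it. For N the half-widths are 8.4, 9.2 and 9.6 points, and the falls (10.4, 13.2, 14.8) exceed them. This is a yardstick only, since no comparison is planned.

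**What each output shows.**

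- Simple proportion by period: single-factor rows and the factor count are planned, so it is partly repaired.
- UC dose outcome and ADD strata: no breakdown by factor. They apply only to Sweden and Germany, because ADD is not assessed in Hungary or the Netherlands.
- Discontinuation and continuation after developing a factor: age is not in the on-treatment VTE list, so they are unaffected.

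**The case against.** **Changes in non-age factors are already displayed.** Each factor is tabulated by period, and the mean count equals the sum of the single-factor proportions. Subtracting the age row gives the mean number of non-age factors, which age cannot mask. This stands for the simple proportion. But factors overlap within patients, so the rows cannot be summed to the share with at least one non-age factor, and a mean count is a different quantity. Neither device reaches the UC outcome or the ADD strata.

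**Two or more factors would serve.** Over 50, it means age plus at least one other factor. But it appears only in Section 9.9, not in Sections 9.3.1, 9.7.1.2.2.1.1 or 9.7.1.3.1, and it misses a patient of 50 or under whose only factor is, for example, a prior VTE. Section 9.3.2 leaves refinement of algorithms and code lists to the SAP, but Table 3 itself fixes which factors count.

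**Age may belong in the headline.** The study measures adherence to the risk minimisation materials, which are not annexed. If they count age, an age-free headline would depart from the recommendation being evaluated. This stands, and is why the composite should be kept.

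A reader might infer more than the protocol supports:

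- *That the composite cannot respond to prescribers.* It can: less prescribing to people over 50 lowers it.
- *That a real change would be nearly invisible.* That depends on an unstated age mix, and at 30% over 50 most of the change survives.
- *That the UC dose outcome is largely a count of UC patients over 50.* No UC age distribution is given.
- *That the loss is greater still.* Halving prevalence at a fixed 65% over 50, with 15% and 35% prevalence, gives falls of 2.6 against 14.0 points. Halving use also shrinks the cohort and shifts its age mix; the same inputs then give 70.3% to 65.4% against 28.0% to 16.3%, or 4.8 against 11.7 points.

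**Conclusion.** The point holds for the composite and for the outcomes that reuse it, not for the VTE analysis as a whole. That age over 50 suffices, and that the composite has a floor at the share over 50, follow from Table 3 without any assumption. The size of the dilution rests entirely on assumed age mix and prevalence: about a fifth to a quarter of the change at 30% over 50, about half at 60%, and just over 70% at 80%.

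The simple proportion is partly protected by the single-factor rows and the factor count. The UC dose outcome and the ADD strata are not protected, and the gap matters most there. The caveat in Section 9.9 covers a flat result in general terms. It covers neither the age component nor a fall produced by the age restrictions. This is a worthwhile, inexpensive improvement; it does not require replacing the planned headline.

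**What to change.** 1. Keep the age-inclusive composite as defined.
2. Add a row for at least one VTE risk factor other than age over 50 to Table 3 and Sections 9.3.1, 9.7.1.2.2.1.1 and 9.7.1.3.1, overall and by VTE Reporting Period.
3. Report that version beside the age-inclusive one in the UC outcome with ADD above 10 mg and in the ADD stratification (Sections 9.3.4 and 9.7.1.2.1).
4. Carry the two-or-more-factor proportion from Section 9.9 into Sections 9.3.1 and 9.7.
5. State in Section 9.9 that age over 50 alone meets the composite, and that a fall may reflect the age restrictions.

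The cost is one derived flag from variables already to be extracted, slightly longer tables, and smaller numerators for the non-age version of the UC outcome. Extraction was planned to start in September 2022, after this protocol version, so the change could be made without rework.
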